10.4. Statistical Analysis Plan

The statistical analysis plan (SAP) will be developed and finalized before database lock and will describe the participant populations to be included in the analyses, and procedures for accounting for missing, unused, and spurious data. This section is a high-level summary of the planned statistical analyses of the primary and secondary endpoints.

10.5. Efficacy Analyses

Table 5. Statistical analysis methods

Endpoint	Statistical Analysis Methods
Primary	Sensitivity and specificity, and ANOVA comparison of Likelihood Ratio test.
Secondary	Difference in sensitivity and specificity between each index assay and Xpert with 95%CI around the difference using methods appropriate for paired data (e.g. Tango score CI)

10.5.1. General Approach

For each test, estimates of sensitivity and specificity will be derived together with 95% confidence intervals. Estimates will be calculated on the overall dataset and by subgroups defined below.

10.5.2. Analysis of Primary Outcomes

Analyses of the diagnostic accuracy of the index test will be done according to the case definitions. Table 6 summarizes the way diagnostic tests results are usually reported when comparing the index test results to a reference standard. Based on the definitions in the table, the following values are defined:

Sensitivity = $TP / (TP + FN)$

Specificity = $TN / (FP + TN)$

Table 6. Definition of classification metrics

Test result	Case definition			
		TB	Non-TB	Total
	Detected	TP	FP	TP + FP
	Not detected	FN	TN	FN + TN
	Total	TP + FP	FP + TN	All

Abbreviations: TB=true positive, FP=false positive, FN=false negative, TN=true negative

Only patients with uncontaminated culture results and without indeterminate test results will be included in the analysis of performance characteristics for MTB detection. Similarly, such patients will contribute to the analysis of the performance characteristics for RIF detection. For each point estimate, a 95% confidence interval will be derived based on Wilson score. Missing data and invalid results will be reported in the descriptive tables, and will not be imputed.

10.5.3. Analysis of Secondary Outcomes

- Accuracy of Truenat MTB assays and RIF assay compared to Xpert MTB/RIF.

The same parameters and sub-groups as for the analysis of primary outcomes will be determined for Xpert MTB/RIF and compared to those of Truenat MTB assays and RIF assay side by side.

- Patient-important outcomes
 - The median time to detection of TB using the Truenat MTB assays will be determined and compared to that of smear, Xpert MTB/RIF, liquid and solid cultures. Furthermore, the median time to detection of RIF resistance using the Truenat RIF assay will be determined and compared to that of phenotypic DST.
 - The number of additional TB (culture-positive) cases detected by the Truenat MTB assays compared to smear and Xpert MTB/RIF.
 - The number of RIF-resistant cases detected using the Truenat RIF assay compared to those detected following the current standard of smear-positive reflexed to Xpert MTB/RIF.

10.5.4. Descriptive statistics

Descriptive statistics tables will be generated to summarize the characteristics of the participants. The number of participants included and excluded will be reported. Among the included participants, the information will be broken down by site, gender, age group, HIV status, history of TB and enrolment group (Case Detection Group and Drug Resistant Group). Results will be reported either in absolute numbers (e.g. number of subjects in a group) or summarized by IQR, percentage.

10.5.5. Additional sub-group analyses

The trial outcomes defined will be also evaluated on the following subpopulations:

- Sensitivity for MTB detection:
 - Per-patient: Truenat MTB assays on S1 and S2 against culture status (based on cultures from S2 and S3)
 - Per-sample processing method: Truenat MTB assays on S1 against culture result on S2 and Truenat MTB assays on S2 against culture result on S2 (same specimen)
 - By smear status
 - By HIV status (where available)
 - On unprocessed (S1) vs decontaminated specimen (S2)
 - After repetition (if result invalid)
 - Compared to Xpert MTB/RIF on S2 (based on culture from S2 and S3)
- Specificity for MTB detection:
 - By TB history
 - By prior TB treatment (> 60 days ago)
 - Compared to Xpert MTB/RIF (based on cultures from S2 and S3)
- Sensitivity and specificity for rifampin resistance detection:
 - Against phenotypic DST
 - Compared to Xpert MTB/RIF on S2 (based on DST from S2 and S3)
- Intermediate/invalid/erroneous results
 - For MTB detection
 - For RIF resistance detection
- Quantitative ability (based on assay cycle threshold (Ct) values)
 - In comparison to culture (positivity and time to positivity, grade for solid culture)
 - In comparison to smear (positivity and grade)

Additional subgroups will be defined and specified in the final SAP.

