8.1. Reference Standard Test and Index Test Procedures

At each site, as per laboratory flow (Figure 2), standard diagnostic algorithms will be followed according to national guidelines and policies of each participating country. If national guidelines cannot be fulfilled using study-specific samples and test results, then an additional spot sputum should be collected.

Sites: All

[figure not shown]

Figure 2. Laboratory workflow

Study spot Sputum 1 (S1) will be collected on Day 1. Approximately 30-60 minutes later, a second spot sputum (S2) will be collected and sent directly to the reference laboratory.

Participants will be given a labelled sputum pot and instructions on how to use it to collect an early-morning sputum (S3), and asked to bring this back to the clinic the next day (Day 2), and provide another spot sputum (S4).

On Day 1, smear microscopy will be performed on Sputum S1 and S2 in the reference laboratory or, if required, in the microscopy centre. In the reference lab, S1 and S2 will be pooled together and homogenised using glass beads and a vortex. Homogenised sputa will be further split: 1.5ml will be used for analysis on raw sputa, and at least 2ml used for NALC-NaOH decontamination.

Briefly, DNA will be extracted independently from i) raw sputum and ii) decontaminated pellet, by the Trueprep Auto device and tested by both the Truenat MTB and the MTB Plus chips, both of which are read by the Truelab UnoDx real-time PCR analyser. All DNA samples testing positive by the MTB assay will be subsequently tested by the Truenat MTB-RIF Dx assay (reflex) which is also read by Truelab UnoDx analyser.

Xpert assays will be performed on the same raw and decontaminated samples.

MGIT and LJ culture will be performed on only on the decontaminated sample.

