On Day 2, morning sputum S3 will be returned to the clinic in a labelled sputum pot and the participant will be asked to provide spot sputum S4. S3 will be sent to the reference laboratory and a second round of MGIT and LJ culture will be performed on decontaminated sample. As for S1 and S2, each positive culture will be identified for MTB complex using MPT64 identification test and/or Line Probe Assay. MGIT SIRE will be used to determine the phenotypic DST for RIF. All samples that exhibit RIF resistance, as determined by either phenotypic DST or Truenat RIF, will be sent for DNA sequencing to determine the mutations responsible for drug resistance. A subset of drug sensitive samples, of approximately matching sample size, will be randomly selected for sequencing, to act as a comparator sequence.

Spot sputum S4 will be processed in the microscopy centre: 500ul raw sputum will be used for DNA extraction by Trueprep Auto and MTB detection by the Truenat assays. Any MTB-positive samples will be subsequently tested by the Truenat MTB-RIF Dx assay (reflex).

The intended objective is to test the Truenat assay in the setting of use (i.e. microscopy centre). If the microscopy centre has an Xpert machine (or if the

microscopy centre and the reference lab are the same), then the Truenat assay need only be performed once along side Xpert (on Day 1).

All leftover pellet, eluate and culture isolates will be stored as per the Manual of Procedures for further testing in case of discordant results e.g. result of Truenat RIF differs from that of phenotypic DST or Xpert MTB/RIF.

Importantly, laboratory technicians performing smear microscopy will be blinded to the results of Truenat MTB assays and other conventional test results. Moreover, the results of the Truenat MTB assays and Truenat RIF will not be reported back to the clinic i.e. will not be used for patient management.

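### Section 10.5.5 defines accuracy analyses on S1-only and S2-only results that the section 8.1 workflow does not produce, and section 10 never names S4, the microscopy-centre specimen

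*Protocol*

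**What the plan says.** The Synopsis sets the primary objective as diagnostic accuracy, against culture and DST, where the test is intended to be used.

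Section 8.1 gives the laboratory flow. For Day 1: "In the reference lab, S1 and S2 will be pooled together and homogenised using glass beads and a vortex". Then: "Homogenised sputa will be further split: 1.5ml will be used for analysis on raw sputa, and at least 2ml used for NALC-NaOH decontamination". Truenat MTB, MTB Plus and Xpert are run on both fractions, and Day 1 culture uses the decontaminated fraction only. S3, the morning specimen, provides the second culture round. For Day 2 testing on site: "Spot sputum S4 will be processed in the microscopy centre: 500ul raw sputum will be used for DNA extraction by Trueprep Auto". The reason is given too: "The intended objective is to test the Truenat assay in the setting of use (i.e. microscopy centre"). One waiver applies: where the microscopy centre has Xpert, or is itself the reference laboratory, Truenat need only be run on Day 1.

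Section 10.5.5 lists analyses by specimen:

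- "Per-patient: Truenat MTB assays on S1 and S2 against culture status (based on cultures from S2 and S3")
- "Truenat MTB assays on S1 against culture result on S2 and Truenat MTB assays on S2 against culture result on S2 (same specimen")
- "On unprocessed (S1) vs decontaminated specimen (S2")
- "Compared to Xpert MTB/RIF on S2 (based on culture from S2 and S3")
- for rifampicin resistance, a comparison with Xpert on S2, with DST taken from S2 and S3.

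Section 10.5.2, the primary analysis, names no specimen. Section 10.5.5 leaves only further subgroups to the SAP.

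**The concern.** The two sections describe different specimens. Section 10.5.5 needs S1 and S2 to have been tested separately, one raw and one decontaminated. Section 8.1 merges them before any Truenat, Xpert or culture work. An analyst given section 10.5.5 and the database would not find the variables it asks for.

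The omission of S4 matters more. The trial exists to show performance at microscopy-centre level, and S4 is the specimen that carries that evidence. The only per-patient specimen definition in section 10 rests on S1 and S2, which are tested in the reference laboratory after bead homogenisation. If no specimen is named in advance for the setting-of-use claim, the choice could be made after results are known, or the reference-laboratory result could stand in for it.

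**Working it through.** No arithmetic decides the point. The check sets section 8.1 beside section 10.5.5; a short calculation then shows what an S4 analysis would cost in precision.

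**1. Specimens produced against specimens analysed**

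| Item in 10.5.5 | Result it needs | Result 8.1 produces |
|---|---|---|
| Per-patient Truenat | Truenat on S1 and on S2 | Truenat on the raw and decontaminated fractions of the S1+S2 pool, and on S4 |
| Per-sample, S1 against culture on S2 | Truenat on S1 alone; culture of S2 alone | Neither exists |
| Per-sample, S2 against culture on S2 | Truenat and culture on S2 alone | Truenat and culture on the pooled decontaminated fraction |
| Unprocessed against decontaminated | S1 raw; S2 decontaminated | Pooled raw; pooled decontaminated |
| Xpert comparison, MTB and RIF | Xpert on S2 | Xpert on pooled raw and pooled decontaminated |
| Patient-level culture and DST | S2 and S3 | Pooled decontaminated fraction and S3 |

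Every row that names S1 or S2 asks for a result that does not exist under that label. The processing and Xpert rows can be recovered by renaming. Items by smear status, HIV status and TB history name no specimen and are not affected by the labels themselves.

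**2. S4**

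S4 appears in sections 8 and 8.1 but nowhere in section 10. Section 4 selected the participating Indian microscopy centres for not having Xpert, so the Xpert limb of the waiver should rarely apply to them.

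**3. Precision if S4 is analysed**

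Inputs from sections 10.2 and 10.5.2: sensitivity 67%, 80 smear-negative/culture-positive cases, target 95% interval width 20 points, TB prevalence 20%, smear-negative share of TB cases 30%, losses 20%, Wilson intervals.

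The plan's own figures first:

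- 80 / (0.20 × 0.30) = 1,333, and 1,333 / 0.8 = 1,666, as stated.
- Wilson width = 2z√[p(1−p)/n + z²/(4n²)] / (1 + z²/n), with z = 1.96 and p = 0.67. At n = 80: 2 × 1.96 × √(0.002764 + 0.000150) / 1.0480 = 0.202 (0.561 to 0.763).
- The smallest n giving a Wilson width of at most 0.20 is 82, against 80 stated. The Wald interval at 80 is 0.567 to 0.773 (width 0.206), which rounds to the protocol's 57 to 77. Either way, 80 gives about 20 points.

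The protocol does not say how many cases would lack a valid S4 result. Taking 0% to 50% as an assumed range:

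- 0% missing, n = 80: width 0.202.
- 20% missing, n = 80 × 0.8 = 64: 2 × 1.96 × √(0.003455 + 0.000234) / 1.0600 = 0.225 (0.548 to 0.773).
- 50% missing, n = 80 × 0.5 = 40: width 0.280 (0.515 to 0.795).

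**The case against.** The best defence is that section 10.5.5 concerns additional subgroup analyses. The primary analysis in section 10.5.2 names no specimen, so it neither selects the pool nor excludes S4. The primary endpoint includes analysis by sample, and S4 is a Truenat-tested sample. Section 10.4 calls the text a high-level summary, and a SAP may well name S4. The glosses in 10.5.5, S1 as unprocessed and S2 as decontaminated, also map readily onto the pooled fractions.

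Much of this stands as a limit on the claim. It does not show that microscopy-centre accuracy will never be estimated, which a reader might infer; it shows that section 10 does not commit to it. Nor does the mismatch make the contrasts unrecoverable. The defence still does not remove the contradiction. The protocol itself fixes the specimens and fixes them against its own workflow, and only further subgroups are deferred. A SAP that follows 10.5.5 inherits the error; one that departs from it contradicts the protocol.

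A reader might also infer that Truenat is credited with two specimens per patient against one Xpert test, biasing the comparison towards Truenat. The documents do not support that. No rule for combining results is stated. Section 8.1 runs Xpert on the same raw and decontaminated material, Table 5 in section 10.5 calls for paired methods, and section 10.5.3 promises the same parameters for Xpert. All three point to matched testing.

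Finally, naming S4 is a design choice with a price. S4 has no culture or Xpert result of its own and may be collected up to 7 days after enrolment. It may also be absent: three specimens suffice under sections 4.1 and 4.4, although sections 4 and 8 ask for four. It cannot be assumed that an S4 result will be on file for every participant.

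**Conclusion.** The point holds as an internal contradiction. The S1-only and S2-only contrasts in section 10.5.5 cannot be computed as labelled under section 8.1. S4, the only specimen assigned to Truenat testing in the setting of use, is not named in section 10. Because the primary objective is accuracy in that setting, this should be corrected before the accuracy data are examined.

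The conclusion rests on the current text of both sections, not on the amendment history or on an unseen SAP. No bias figure attaches to it. The only sizes are the S4 interval widths, from 0.202 with all 80 cases to 0.280 with half of them, and the missing fractions behind them are assumptions.

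**What to change.** Reconcile section 10.5.5 with section 8.1, and carry the same definitions into the SAP:

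1. Name as the setting-of-use analysis Truenat MTB, and separately MTB Plus, on raw S4 at the microscopy centre, against patient-level culture from the pooled S1/S2 decontaminated fraction plus S3.
2. Relabel the S1-versus-S2 contrasts, rather than delete them, as pooled raw versus pooled decontaminated, both against that same culture standard. Correct the culture and DST sources in the MTB and RIF items in the same way.
3. State that Xpert comparisons are like-for-like on the same pooled fraction: raw with raw, pellet with pellet.
4. Report separately the sites where section 8.1 waives S4 testing, and give the number of participants without a valid S4 result.

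The change is to wording and uses tests already planned. Its cost is some precision in the S4 estimate where S4 is missing, plus an added table of S4 availability.

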10.5.6. Planned Interim Analyses

No interim analysis is planned. Continued data monitoring will be performed (see section 12 Data handling and record keeping).

10.6. Safety Analyses

Not applicable. Given the nature of this trial i.e. diagnostic accuracy and comparison of diagnostic solutions, the probability of an AE and SAE to be associated with the investigational products is exceedingly rare. Therefore, no safety analysis will be conducted. However, AE and SAE will be reported as per Section 9 Safety and incident reporting.

10.7. Independent Data Monitoring Committee (IDMC)

Not applicable. Based on FIND internal procedures, an IDMC will be established only for trials where participants are at greater than minimal risk e.g. invasive techniques for specimen collection or use of index test results to inform patient care.

11. Regulatory and Ethical Considerations

11.1. Regulatory and Ethics Approvals

This trial will be conducted in accordance with the protocol and with the following:

- Consensus ethical principles derived from international guidelines including the Declaration of Helsinki
- Applicable ICH Good Clinical Practice (GCP) Guidelines
- Applicable laws and regulations

The protocol, protocol amendments, ICF and other relevant documents (eg, advertisements) must be submitted to an IRB/IEC by the investigator and reviewed and approved by the IRB/IEC before the trial is initiated.

- Any amendments to the protocol will require IRB/IEC approval before implementation of changes made to the trial design, except for changes necessary to eliminate an immediate hazard to trial participants.
- The investigator will be responsible for the following:

- Providing written summaries of the status of the trial to the IRB/IEC annually or more frequently in accordance with the requirements, policies, and procedures established by the IRB/IEC
- Notifying the IRB/IEC of SAEs or other significant safety findings as required by IRB/IEC procedures
- Providing oversight of the conduct of the trial at the site and adherence to requirements of ICH guidelines, the IRB/IEC, the WHO Good Clinical Laboratory Practice (GCLP), European regulation 536/2014 for clinical studies (if applicable), and with applicable national regulations.

11.2. Financial Disclosure

Investigators and sub-investigators will provide FIND with sufficient, accurate financial information as requested to allow FIND to submit complete and accurate financial certification or disclosure statements to the appropriate regulatory authorities. Investigators are responsible for providing information on financial interests during the course of the trial and for 1 year after completion of the trial.

11.3. Informed Consent Process

- The investigator or his/her representative will explain the nature of the trial to the participant or his/her legally authorized representative and answer all questions regarding the trial.
- Prospective participants must be informed that their participation is voluntary and will be required to sign and date a statement of informed consent that meets the requirements of local regulations and/or ICH guidelines where applicable, and the IRB/IEC or trial centre.
- The medical record must include a statement that written informed consent was obtained before the participant was enrolled in the trial and the date the written consent was obtained. The authorized person obtaining the informed consent must also sign the ICF.
- Illiterate patients must provide a thumbprint on the ICF and the ICF must be signed and dated by an impartial witness.
- Participants must be re-consented to the most current version of the ICF(s) during their participation in the trial.

11.4. Data Protection

- Participants will be assigned a unique identifier by FIND. Any participant records or datasets that are transferred to FIND will contain the identifier only; participant names or any information which would make the participant identifiable will not be transferred.
- The participant must be informed that his/her personal trial-related data will be used by FIND in accordance with local data protection law. The level of disclosure must also be explained to the participant.
- The participant must be informed that his/her medical records may be examined by Clinical Quality Assurance auditors or other authorized personnel appointed by FIND, by appropriate IRB/IEC members, and by inspectors from regulatory authorities.

11.5. Subject Confidentiality

The Principal Investigator will be responsible for the recording of all subject's personal details, screening number and unique trial number in the Subjects Identification List. To ensure confidentiality, this list must be kept in a place, with access restricted to authorized trial staff. All laboratory specimens, including stored specimens, as well as trial reports, data collection tools, and administrative forms will be identified by a using the patient's unique trial number. Names will not be used on any of these documents. All local databases will be secured with password-protected access systems. The Investigator must ensure anonymity of the patient and ensure that all documents are anonymised before being transmitted to FIND.

11.6. Other ethical considerations

11.6.1. Use of stored specimens:

Sputum volume after processing as well as Trueprep used chips will be stored temporarily in case further testing is deemed to be necessary. Samples will be labelled with a trial identifier; the specimens will be linked to results of other mycobacteriology tests, the final trial diagnosis (e.g. non-TB case, culture-positive TB case, clinical TB case, Indeterminate) of the participant. Specimens will be stored temporarily at the sites. Further testing may be required at a Reference Laboratory or specialized research laboratories. An export permit will be obtained accordingly if required. Moreover, after trial completion leftover well-characterised specimens could be used for future research of product development as long as trial participants have agreed to this during the initial visit.

11.6.2. Protocol deviations

Protocol deviations occur when there is non-adherence to the Protocol and includes Informed Consent, enrolment, and other occurrences of non-adherence to the Protocol. Protocol deviations should be sent to the local IRB/IEC per the local IRB/IEC guidelines. Any protocol deviation that meets reporting requirements of the local IRB/IEC will also be reported with the same timeliness to the FIND project manager.

11.6.3. Termination of the Trial

Given the nature of the trial, termination due to safety or other reasons is not anticipated. However, should the trial be terminated, participants will be referred to the appropriate local health service for TB evaluation and care. If positive for MTB, results of conventional microbiological tests (i.e., sputum smear microscopy and mycobacterial cultures) will be reported to appropriate local health authorities in accordance with local public health reporting regulations.

